## Document History

Document	Version
Original protocol	1.0
Amendment 1	2.0

Amendments incorporate all revisions to date, including amendments made at the request of country health authorities, institutional review boards/ethics committees (IRBs/ECs), etc.

## Summary of Changes

### Amendment 1

The purpose of this non-substantial amendment is to clarify that the 125 number of subjects refers to eligible enrolled subjects throughout the protocol. An eligible subject is one who confirms that they have nasal congestion of severity 5, which they wish to treat, once they have received the product. These changes are listed in the table below.

Section	Original	Revision
1.1 Synopsis (Page 12: Study Design)	The study expects to enroll 125 subjects to ensure that 100 subjects complete the study.	The study expects to enroll 125 eligible subjects. A total of 100 subjects are expected to complete the study.
12.1 Synopsis (Page 14: Type and Planned Number of Subjects)	It is anticipated that a total of 125 eligible subjects will be enrolled.	This study intends to enroll approximately 125 eligible subjects.
4.1 Overall Design (Page 19)	The study expects to enroll approximately 125 subjects to ensure that 100 subjects complete the study.	The study intends to enroll approximately 125 subjects. A total of 100 subjects are expected to complete the study.
5.1 Type and Planned Number of Subjects (Page 22)	It is anticipated that a total of 125 eligible subjects will be enrolled into the trial.	This study intends to enroll approximately 125 eligible subjects.
12.1 Sample Size Determination (Page 43)	
Sufficient individuals will be screened to enroll approximately 125 healthy subjects assuming an estimated 20% drop out rate.
 
Using the above parameters, we obtain a sample size N =125 subjects to retain 100 completed subjects.
	
Sufficient individuals will be screened to enroll approximately 125 healthy eligible subjects assuming an estimated 20% drop out rate.
 
Using the above parameters, we obtain a sample size N =125 eligible subjects to retain 100 completed subjects.

## 1 PROTOCOL SUMMARY

### 1.1 Synopsis

**Short Title:**

Otrivine: QoL impact in a real-world setting

**Background and Rationale:**

This study is designed to generate real world data from subjects with nasal congestion acquired from common cold following treatment with a marketed nasal spray. The main aim of this study is to evaluate the effectiveness of a nasal spray on quality of life (QoL) factors.

**Objectives and Endpoints:**

Objective(s)	Endpoint(s)
Primary	
To evaluate the over-time effects of Otrivine on QoL factors and common cold symptoms among individuals experiencing nasal congestion associated with common cold, following up to 7 days of treatment using WURSS-21.	
Scores over time on Days 0, 1, 2, 3, 4, 5, 6, 7 in:
 
 
- WURSS-21 total score
 
- WURSS-21 total symptom domains
 
- WURSS-21 total QoL domains
 
- Each of the WURSS-21 symptom domains (10 in total)
 

Secondary	
To evaluate the over-time effects of Otrivine on additional measures of QoL factors among individuals experiencing nasal congestion associated with common cold, following up to 7 days of treatment, using additional QoL factors.	
Post Otrivine use score on Days 1, 2, 3, 4, 5, 6, 7, for each of the following additional health related QoL factors:
 
 
- snoring
 
- alertness the morning after
 
- feeling self-conscious about how you sound
 
- smell
 
- taste
 
- feeling self-conscious around people
 
- energy
 
- motivation
 

Safety	
To record adverse events (AEs) during study period	
Number and percent of patients reporting AEs or serious AEs (SAEs) while on treatment
 
 
• Related to product
 
• Not related to product
 

## **Study Design:**

This is a longitudinal, open-label study evaluating the effect on QoL factors in subjects with the common cold using Otrivine nasal spray (xylometazoline hydrochloride 0.1%), in a real-world setting. A sufficient number of adults aged 18 years and over with symptoms of common cold will be screened for eligibility. The study expects to enroll approximately 125 eligible subjects. A total of 100 subjects are expected to complete the study.

Subjects will be recruited through targeted advertising on social media channels. This study is entirely decentralized, and subjects will not be required to physically attend any on-site visits. All study data will be collected remotely through a study app using the subject's own mobile device.

### ***Pre-screening & Informed Consent***

Adult subjects reporting early symptoms of the common cold including nasal congestion and at least one other common cold symptom (scratchy throat, sore throat, dry cough or watery nasal discharge) within the previous 24 hours, who respond to a social media ad, complete the pre-screening questionnaire, and are seeking relief of their nasal congestion symptoms, and are eligible to take part in the study will be sent an email invitation to download the study app and complete the study registration process.

Once in the study app, an electronic informed consent (eIC) interview phone call will be scheduled, and investigator/designee will release the eIC form that will be made available to the subject through the study app. During the eIC phone call subjects will have the opportunity to ask any questions they may have. Subject identification will be checked during the consent interview phone call. Subjects that sign the eIC form will have the option to download the signed eIC to save a copy for local reference and/or access the signed eIC through the study app once the investigator/designee countersigns and attests that the consent interview phone call was completed.

### ***Screening & Baseline Assessments***

Subjects that provide informed consent will be asked to complete the Wisconsin Upper Respiratory Symptom Survey (short version) (WURSS-21) and, if eligible, they will be prompted to complete the screening questionnaire, confirm their medical history and concomitant medication via a phone call with the investigator/designee, and complete their demographics and shipping form. If the responses to all screening criteria are fulfilled, the subject will be considered enrolled and will move forward to training on how to use the study app. Once this training is complete, they will complete the additional QoL questions as baseline assessments.

Upon completion of baseline assessments and questionnaires, the subject will be shipped the study product. Once the shipment is received, the subject will need to confirm receipt and usability of the product via the app.

### ***Treatment Period***

Upon receipt of the study product, the subjects will re-confirm their eligibility to continue in the study based on the previous screening criteria including completion of the WURSS-21 questionnaire (see appendix section 15.2.1). Those with nasal congestion (described as plugged nose on WURSS-21) of at least moderate (score 5) based on WURSS-21 and who exhibit at least one other common cold symptom of at least mild (score 3) based on WURSS-21 and who self-select to treat their nasal congestion symptoms, will be asked to start treatment with the product according to the label instructions.

Subjects who do not satisfy these criteria will be considered dropouts.

Each morning the subject will be prompted to complete the WURSS-21 questionnaire, the additional QoL questions (considering the effects of the product used during the day before).

### ***End of Treatment Period***

As per leaflet instruction, xylometazoline hydrochloride (0.1%) nasal spray may be used for up to 7 treatment days.

Subjects will have the option to discontinue treatment at their discretion. The reasons for discontinuing treatment will be captured in the app whenever possible.

Subjects may choose to discontinue treatment if:

- they feel that their symptoms do not warrant further use of the study product
- their nasal symptoms/congestion is considered resolved

Subjects that continue to use the study product will be prompted to discontinue treatment after 7 days of continuous use and seek advice from their general practitioner for further assessment and treatment.

Subjects will also be informed that the study will end on Day 7 (or the day after the last treatment, if earlier than 7 days), and will be asked to fill in an exit survey.

### ***Study Product:***

Otrivine Congestion Relief 0.1% Nasal Spray (Xylometazoline Hydrochloride), Menthol (UK Marketplace)

Product code: **CCI**

The study product is to be used as per leaflet instructions: 1 spray in each nostril up to 3 times per day until resolution of symptoms or up to a maximum of 7 days, whichever occurs first. This product is currently on the market for over-the-counter consumer purchase in the United Kingdom.

**Type and Planned Number of Subjects:**

Adult subjects aged 18 years and over, reporting early symptoms of the common cold including nasal congestion and at least one other common cold symptom (scratchy throat, sore throat, dry cough or watery nasal discharge) within the previous 24 hours will be screened for enrollment into the study. The study intends to enroll approximately 125 eligible subjects. This study assumes an approximate 20% drop out rate. A total of 100 subjects are expected to complete the study.

**Statistical Analyses:**

**Sample size:** The sample size determination was performed using a non-parametric Paired Wilcoxon test. The sample size is based on a significance level ( $\alpha$ ) of 0.05, 80% power ( $1-\beta$ ) and an estimated standardized effect size of 0.27.

**Population for analysis:** A modified intention-to-treat (mITT) analysis will be performed and will include all subjects who received at least one dose of the study product and have at least one post-baseline QoL questionnaire data to support at least one of the primary endpoint assessments. Primary and secondary analyses will be summarized using the mITT population only. Safety population will include all subjects who receive at least one dose of study product. Adverse events will be summarized using the Safety population.

## 1.2 Schedule of Activities:

Schedule of activities tables provide an overview of the study procedures.

**Table 1-1 Schedule of Activities**

Procedure/ Assessment	Screening/ Baseline	Day 0	Day 1	Day 2	Day 3	Day 4	Day 5	Day 6	Day 7
Informed Consent	x								
Screening Questionnaire	x								
Demographics	x								
Subject eligibility	x								
Enrollment	x								
WURSS-21 questionnaire (baseline, pre-treatment)	x								
Additional QoL Questions (baseline, pre-treatment)	x								
Study product shipped a	x								
Confirmation of eligibility b		x							
Study product treatment usage c		x	x	x	x	x	x	x	
WURSS-21 questionnaire (post-treatment) d			x	x	x	x	x	x	x
Additional QoL Questions (post-treatment) e			x	x	x	x	x	x	x
Subject diary completion			x	x	x	x	x	x	x
Change in Medication Reporting			x	x	x	x	x	x	x
Adverse Event (AE) Review f		x	x	x	x	x	x	x	x
End of symptoms reporting g									x
End of study questions									x
Study Conclusion and/or Subject Exit from Study h									x
Medical History i	i_x								
Concomitant Medication i,j	i_x	j_x							
Return of used/unused product k									x

**Footnotes:**

a Study product (Otrivine Congestion Relief 0.1% Nasal Spray) will be shipped only after baseline assessments and questionnaires have been completed.

b Confirmation of eligibility means WURSS-21 (plugged nose at least moderate, cold symptoms at least mild) AND blocked nose that they still wish to treat.

c 1 spray in each nostril up to 3 times per day and up to 7 days or until resolution of symptoms, whichever occurs first.

d WURSS-21 (post-treatment) will be completed each day in the morning.

e Additional QoL questions (post-treatment) will be asked each day in the morning.

f Adverse Events (AEs) and therefore all Serious Adverse Events (SAEs) will be collected immediately from the time of first use of the product by the PI/designee.

g End of study reporting will occur upon resolution of symptoms or Day 8 (whichever is sooner).

h Study Conclusion and/or Subject Exit from Study will occur at subject's completion of study or resolution of symptoms, whichever occurs first.

i Once subjects are eligible for enrolment into the study, the PI/designee will record the subjects medical history and concomitant medication use via a phone call scheduled through the study app. Subjects will be given an opportunity to report any changes in health, concomitant medications, or non-drug treatments/procedures.

j Subjects will be given an opportunity to report any changes in health, concomitant medications, or non-drug treatments/procedures.

k Will be returned to **CCI** via a pre-paid package.

## 2 INTRODUCTION

### 2.1 Study Rationale

Real world evidence (RWE) studies offer an opportunity to gather information of a marketed product in real-world heterogeneous populations that can complement clinical evidence, consumer insight data, and post-marketing surveillance. Real world data (RWD) generation is increasingly important in determining effectiveness outside of the tightly controlled conditions of randomized clinical trials (RCTs), that do not always reflect real-world patient populations, limiting their generalizability and external validity (Sherman et al., 2016)

This study is designed to generate real world data from subjects with nasal congestion associated with the common cold, evaluating the effects of a commercially available nasal spray on health-related quality of life.

In line with UK Regulations informed consent will be conducted via a phone call with the investigator/designee and subjects will be instructed to return the study product after treatment discontinuation or on Day 7 in a self-addressed envelope/packet.

Otrivine is a marketed nasal decongestant spray used for treatment of nasal congestion associated with common cold. Although this is a non-life-threatening condition, it impacts individuals' ability to function normally in day-to-day activities (physical, social, occupational, and emotional).

Based on a large national on-line survey conducted in the United States (ACHOO survey) (Blaiss et al., 2015, Dicpinigaitis et al., 2015), nasal congestion was one of the most bothersome symptoms of the common cold; and it has been shown to have a significant impact on the quality of life, work productivity, absenteeism, and sleep quality.

This study will generate data to support the decongestant effectiveness of the Otrivine nasal spray in the real-world setting among individuals with common cold to understand how the effect can influence their quality of life.

### 2.2 Background

Otrivine (xylometazoline hydrochloride) is a nasal decongestant spray that constricts nasal blood vessels and increases nasal airflow, enabling individuals with a blocked nose to breathe more easily. This is a well-known and commonly used decongestant; different versions of this product have been marketed in numerous countries and used by consumers for decades.

A double-blind, placebo-controlled, parallel group study by Eccles (Eccles et al., 2008) investigated the efficacy of the Otrivine nasal spray in patients with common cold. Twenty-nine patients were treated with xylometazoline hydrochloride 0.1%, and 32 patients treated with a placebo (saline solution); 1 spray 3 times a day for up to 10 days was the posology used. The primary objective of the study was to determine the

decongestant effect (via nasal conductance); and the secondary objectives were to determine the peak subjective effects (visual analog scale), duration of relief of nasal congestion and total and individual cold symptoms. In addition, any effects on sleep, tiredness, general well-being and smell/taste were studied as exploratory variables with a daily diary. Adverse events (AEs) were also assessed. The decongestant effect of xylometazoline hydrochloride was significantly greater than placebo, as shown by the nasal conductance at 1 hour. Peak subjective effect (VAS assessment) was also significantly positive. Nasal conductance was significantly superior for up to 10 hours. Compared with placebo, xylometazoline hydrochloride significantly improved the total common cold symptom score on day 1 of treatment (xylometazoline hydrochloride 25.71 versus placebo 35.79; ( $p=0.0221$ )) and significantly improved individual common cold symptoms on day 1 (blocked nose, sore throat, and earache), day 2 (blocked nose), day 5 (runny nose), and day 10 (runny nose) of treatment. Xylometazoline hydrochloride-associated significant improvement of total and some individual common cold symptoms scores lead to significantly greater patient general evaluation and satisfaction with treatment.

Although common cold symptoms are usually mild, they represent a huge burden for society in terms of impaired QoL and economic losses (Passioti et al., 2014, Heikkinen and Jarvinen, 2003). While rhinoviruses are the predominant cause of the common cold, the aetiological agent remains unknown in up to half of all upper respiratory tract infections (URTIIs) (Stein, 2017). For the common cold, only symptomatic treatments exist (Passioti et al., 2014, Stein, 2017). Most people require no prescription medications or doctor visits but do use a variety of over-the-counter (OTC) medications for relief of symptoms.

### 2.3 Mechanism of Action/Indication

Otrivine nasal spray contains 0.1% of xylometazoline hydrochloride as active ingredient. It is a direct-acting sympathomimetic that acts on alpha-adrenergic receptors on the nasal blood vessels to quickly reduce swelling in the nose, help drain the sinuses and relieve nasal congestion.

## 3 STUDY OBJECTIVES AND ENDPOINTS

Table 3.1 Study Objectives and Endpoints

Objective(s)	Endpoint(s)
Primary	
To evaluate the over-time effects of Otrivine on QoL factors and common cold symptoms among individuals experiencing nasal congestion associated with common cold, following up to 7 days of treatment using WURSS-21.	
Scores over time on Days 0, 1, 2, 3, 4, 5, 6, 7 in:
 
 
- WURSS-21 total score
 
- WURSS-21 total symptom domains
 
- WURSS-21 total QoL domains
 
- Each of the WURSS-21 symptom domains (10 in total)
 

Secondary	
To evaluate the over-time effects of Otrivine on additional measures of QoL factors among individuals experiencing nasal congestion associated with common cold, following up to 7 days of treatment, using additional QoL factors.	
Post Otrivine use score on Days 1, 2, 3, 4, 5, 6, 7, for each of the following additional health related QoL factors:
 
 
- snoring
 
- alertness the morning after
 
- feeling self-conscious about how you sound
 
- smell
 
- taste
 
- feeling self-conscious around people
 
- energy
 
- motivation
 

Safety	
To record adverse events (AEs) during study period	
Number and percent of patients reporting AEs or serious AEs (SAEs) while on treatment
 
 
• Related to product
 
• Not related to product
 

Property of GSK Consumer Healthcare - Confidential

May not be used, divulged, published or otherwise disclosed without the consent of GSKCH

## 4 STUDY DESIGN

### 4.1 Overall Design

This is a longitudinal, open-label study evaluating the effect on QoL factors in subjects with the common cold using Otrivine nasal spray (xylometazoline hydrochloride 0.1%), in a real-world setting. A sufficient number of adults aged 18 years and over with symptoms of common cold will be screened for eligibility. The study intends to enroll approximately 125 eligible subjects. A total of 100 subjects are expected to complete the study.

Subjects will be recruited through targeted advertising on social media channels. This study is entirely decentralized, and subjects will not be required to physically attend any on-site visits. All study data will be collected remotely through a study app using the subject's own mobile device.

#### ***Pre-screening & Informed Consent***

Adult subjects reporting early symptoms of the common cold including nasal congestion and at least one other common cold symptom (scratchy throat, sore throat, dry cough or watery nasal discharge) within the previous 24 hours, who respond to a social media ad, complete the pre-screening questionnaire, and are seeking relief of their nasal congestion symptoms, and are eligible to take part in the study will be sent an email invitation to download the study app and complete the study registration process.

Once in the study app, an electronic informed consent (eIC) interview phone call will be scheduled, and investigator/designee will release the eIC form that will be made available to the subject through the study app. During the eIC phone call subjects will have the opportunity to ask any questions they may have. Subject identification will be checked during the consent interview phone call. Subjects that sign the eIC form will have the option to download the signed eIC to save a copy for local reference and/or access the signed eIC through the study app once the investigator/designee countersigns and attests that the consent interview phone call was completed.

#### ***Screening & Baseline Assessments***

Subjects that provide informed consent will be asked to complete the Wisconsin Upper Respiratory Symptom Survey (short version) (WURSS-21) and, if eligible, they will be prompted to complete the screening questionnaire, confirm their medical history and concomitant medication via a phone call with the investigator/designee, and complete their demographics and shipping form. If the responses to all screening criteria are fulfilled, the subject will be considered enrolled and will move forward to training on how to use the study app. Once this training is complete, they will complete the additional QoL questions as baseline assessments.

Upon completion of baseline assessments and questionnaires, the subject will be shipped the study product. Once the shipment is received, the subject will need to confirm receipt and usability of the product via the app.

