## 8 STUDY PROCEDURES

This section lists the procedures to be completed for each planned study time point. However, as per nature of RWE studies, if a subject fails to complete their daily questionnaires at any timepoint post-baseline, subjects will be permitted to continue in the study. The timing of each procedure is listed in the [Schedule of Activities](#) section.

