## 8.2 Study Period

### 8.2.1 Days 0-7

The number of days each subject will actively engage with the study will vary according to the resolution of their nasal symptoms. Subjects will use the nasal spray for up to 7 days (as per leaflet instructions) unless their nasal symptoms resolve prior to that. If symptoms and subject reporting continues for the full 7 days, subjects will complete the questionnaire for 7 days (baseline + 6 post treatment days). Subjects with nasal symptoms resolved sufficiently to no longer warrant product use or those who determine they no longer wish to medicate for nasal congestion symptoms will complete daily forms from baseline through one day after the last dose of study. This will complete their “study period”.

The following assessments will be completed in the study app during the study period:

- Subjects will report any changes in health, concomitant medications, or non-drug treatments/procedures
- Subjects will complete WURSS-21 questionnaire and additional QoL questions each day
- Subjects will complete an eDiary to record product use each day
- Subjects will report any adverse events
- Subjects will report the end of nasal symptoms (or sufficiently reduced)/stop of product use and answer end of the study questions prior to exiting the study

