### **9.2 Quality of Life Assessments**

The following quality of life tools will be completed by subjects daily the study app from receipt of product to study conclusion.

- WURSS-21 Questionnaire
- Additional QoL Questions (in appendix section 15.2.2)

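### The additional QoL baseline is scheduled only before the product ships, so the pre/post comparison in Section 12.3.2 includes an untreated interval of unstated length

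*Protocol*

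**What the plan says.** Section 4.1 (repeated in the synopsis) has subjects complete WURSS-21, the screening questionnaire, a medical-history call, the forms and the app training. Then come the eight additional QoL items: "Once this training is complete, they will complete the additional QoL questions as baseline assessments". Only after that is the product sent. Footnote a to Table 1-1 confirms the order: the product "will be shipped only after baseline assessments and questionnaires have been completed".

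In Table 1-1 the row "Additional QoL Questions (baseline, pre-treatment") has a single mark, under Screening/Baseline. The post-treatment row is marked on Days 1 to 7. Neither row is marked on Day 0. For Day 0, footnote b states "Confirmation of eligibility means WURSS-21 (plugged nose at least moderate, cold symptoms at least mild") together with a blocked nose that the subject still wants to treat. The Treatment Period text in Section 4.1 likewise mentions only WURSS-21 and the choice to treat.

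Two other sections point a different way. Section 8.2.1, headed Days 0-7, says "Subjects will complete WURSS-21 questionnaire and additional QoL questions each day", and that subjects who stop early "will complete daily forms from baseline through one day after the last dose of study". Section 9.2 says both questionnaires "will be completed by subjects daily the study app from receipt of product to study conclusion". Section 8, however, defers to the Schedule of Activities: "The timing of each procedure is listed in the" Schedule.

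Section 12.3.2 takes each subject's pre-treatment score as the yardstick for the effect of Otrivine and names no day for it. The secondary endpoint lists Days 1 to 7; the primary WURSS-21 endpoint lists Days 0 to 7.

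**The concern.** A pre-treatment score should describe the subject just before the first dose. Here the only scheduled one is taken before the product leaves the depot, early in an illness that the protocol itself describes as changing quickly. Whatever happens between that answer and first use is counted as part of the product's effect.

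If subjects worsen in that interval, improvement is understated. If the spray arrives after the peak, natural recovery is credited to it. Section 4.2 counts on subjects having treatment at hand when nasal symptoms peak, so as to reduce confounding; a baseline taken before shipping works against that aim.

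This cannot be repaired in the analysis. A SAP may choose which recorded score counts as baseline, but it cannot supply a Day 0 answer that was never collected.

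**Working it through.** The plan gives no figure on this point to reproduce, so the check sets the passages side by side and then works out what follows.

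**Is a pre-dose Day 0 answer scheduled?**

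- Table 1-1: pre-treatment form at Screening/Baseline only; post-treatment form on Days 1 to 7. Day 0: neither.
- Footnote a and Section 4.1: baseline answers come before shipping.
- Footnote b and Section 4.1 (Treatment Period): Day 0 repeats WURSS-21 and the wish to treat.
- Sections 8.2.1 and 9.2: can be read as including Day 0. Neither says which form would be used or that the answer is the baseline.
- Section 15.2.2: the post-treatment form asks about the time after using the product and is given in the morning, so it cannot serve as a pre-dose answer. The pre-use form is scheduled only before shipping.
- Section 8.2.1 also counts seven questionnaire days, baseline plus six post-treatment days. That hints at a baseline inside the study period but does not say Day 0. It also disagrees with the seven post-treatment days (Days 1 to 7) in Table 1-1.

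**Is the interval bounded?** Inclusion criterion 5 limits onset-to-screening to 24 hours. Criterion 6 concerns confirmation within 24 hours of receipt. Neither limits the time from screening to receipt.

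**Effect of drift.** Assume a higher score is worse; the response scale of these eight items is not legible in the text. Let d = Day 0 score − screening score. Then

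Screening − Post = (Day 0 − Post) − (Day 0 − Screening) = (improvement from Day 0) − d.

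So d points of worsening before Day 0 lower the apparent improvement by d, and d points of recovery raise it by d.

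**Where first use falls.** Inputs: onset 0 to 1 day before screening starts (criterion 5); stated peak 1 to 3 days after first appearance (Section 2.2). Let L be the days from the baseline answers to first use. L is assumed, and the answers are assumed to be given on the day screening starts. Time from onset to first use = (0 to 1) + L.

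| L (assumed) | Onset to first use | Against a peak of 1 to 3 days |
|---|---|---|
| 1 day | 1 to 2 days | within |
| 2 days | 2 to 3 days | within |
| 3 days | 3 to 4 days | at its end or past it |

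**Recall window.** The baseline form looks back 24 hours (Section 15.2.2). Its overlap with the 24 hours before first use is max(0, 24 − gap). A gap of 12 hours gives 24 − 12 = 12 hours, or 50%. A gap of 24 hours or more gives 0.

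**Contrast with an item that is re-checked.** Treated subjects must score at least 5 for plugged nose, on a scale ending at 7, both at screening and on receipt. That item can therefore drift by at most 7 − 5 = 2 points. The eight additional items have no such restriction.

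**The case against.** The strongest reply is that the text already supports Day 0 collection. Section 9.2 starts both questionnaires at receipt of the product, which is when the Day 0 re-confirmation takes place, and Section 8.2.1 covers Days 0-7. On that reading the fault is an inconsistency with Table 1-1, and no data are lost. The app-workflow figures, which might show Day 0 tasks, are not visible in the text reviewed. This has weight: the two readings do coexist, and the loss follows only if the Schedule is applied. But Section 8 sends the reader to the Schedule, the Schedule is legible, and the only form suited to a pre-dose answer is placed before shipping.

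A second reply is that naming the baseline belongs in the SAP, which was not available for this review. That is fair as far as definition goes. It does not cover collection, which the protocol fixes.

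Third, the impact is narrow. The secondary endpoint is the post-use score, Section 12.3.2 promises daily medians, no change-score test is specified there, and this is a single-arm study whose protocol already concedes confounding by natural resolution. All of that stands and limits the weight of the point. Even so, Section 12.3.2 says the pre-treatment score will be used to determine the effect.

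Finally, delivery times are assumed, and neither the size nor the direction of drift is known. The plugged-nose bound belongs to WURSS-21 and says nothing about how far the QoL items actually move. These limits stand too.

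**Conclusion.** The concern holds. The only scheduled pre-treatment answers to the additional QoL questions precede shipping, Sections 8.2.1 and 9.2 do not agree clearly with Table 1-1, and no passage names a Day 0 score as the reference for Section 12.3.2. On the Schedule's reading, the comparison for the secondary objective contains an untreated interval of unstated length near the stated symptom peak.

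The bias equals the drift in that interval, point for point. Its size and direction cannot be given, because the delivery time and the natural change in these items are not in the document. The placement of first use at 1 to 4 days after onset rests on the assumed 1 to 3 days from baseline to first use. The post-treatment medians are unaffected, and the primary endpoint already has a Day 0 WURSS-21. This is an inexpensive improvement to a secondary comparison and does not threaten the main result.

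**What to change.** - **Table 1-1 and Section 4.1** (and the matching synopsis text): add the eight pre-use questions to Day 0, answered before first use alongside the re-confirmation WURSS-21. Keep the pre-shipping answers as screening values.
- **Section 12.3.2:** name the Day 0 pre-dose score as the pre-treatment score.
- **Sections 8.2.1 and 9.2:** align with the Schedule, including the count of questionnaire days.
- **For consistency:** state in Section 12.3.1 that the Day 0 WURSS-21, already in the primary endpoint, is the pre-treatment value, and relabel the screening WURSS-21 row in Table 1-1.

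The cost is eight app questions on one day when the subject is already in the app (about a minute each subject, an assumption), one Schedule row and short text edits. The change removes only the pre-dose interval; natural resolution after first use still confounds the single-arm comparison.
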